**Table 1**

Age	Enuretic	Non Enuretic	% Enuretic
5-10	8	28	22.2%
11-21	9	18	33.3%
Total	17	46	27 %

Our initial objective was to conduct a randomized placebo controlled double blinded study to assess the efficacy of desmopressin on the rate of nocturnal enuresis in patients with SCD compared to placebo. We also planned to utilize quality of life and fatigue scale questionnaires to evaluate the quality of life in these patients prior to and after treatment. We hypothesized that patients receiving desmopressin would demonstrate fewer episodes of nocturnal enuresis compared to those receiving placebo. Due to low accrual with the study (five participants completed the study and nine participants withdrew from the study), and due to the fact that DDAVP treatment for nocturnal enuresis is already standard of care in a general pediatric population, it was determined beneficial by the investigators to prescribe DDAVP as standard of care and to eliminate the placebo group. The study team will prospectively collect quality of life data for the patients prior to prescribing DDAVP and then one month after initiating treatment with DDAVP. Prior to starting DDAVP an eligibility diary would be filled out on recollection by patient on their enuresis patterns for the past 2 weeks (Appendix 1A). Enuresis diaries would be given to patients and families to track their enuresis but also could be filled out retrospectively with study coordinator either in person or over the phone. We propose to then analyze their laboratory, physical exam, imaging, data prospectively for those patients administered DDAVP as part of their clinical care upon starting the DDAVP. We would prospectively administer surveys on willing participants prior to starting DDAVP and then one month into the intervention. To provide information to the sickle cell research community we propose the following interventions.

The primary objective of this study is:

1. To prospectively assess if the use of desmopressin in patients with sickle cell disease and nocturnal enuresis will decrease the number of nighttime episodes of enuresis by 50% after initiating DDAVP at 0.4 mg nightly dose with dose escalation as clinically appropriate.

Secondary objectives are:

1. To determine if patients with sickle cell disease and nocturnal enuresis receiving desmopressin will have an improved quality of life compared to their baseline.

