### **Enrollment:**

This study will be a cohort analysis of a standard of care medication administered for nocturnal enuresis. Prior to starting this standard of care medication patients will fill out the PROMIS questionnaire on fatigue. Patients with sickle cell disease who fit the inclusion criteria will be notified about the study when they are seen in hematology clinic, prior to discharge from hospitalization or via phone by study staff. Patients enrolled during hospitalization will not start the trial until a post-hospitalization follow up visit. At this point, the study will be introduced and discussed. Written consent for the survey will be obtained from interested and eligible guardians, or patients, if they are older than 18 years old or an emancipated minor. Patients 7-17 years of age will sign assent. Patients will also be identified for eligibility via the electronic medical record. Patients who fit the inclusion criteria will be called and informed of the medication following a detailed script (see Appendix 6). If they are interested, consent will be obtained at the next outpatient or inpatient visit. Patients and/or guardians will have the option to decline participation or opt out of the study at any point.

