### **Monitoring**

Patients will be asked to keep an “enuresis diary” for four weeks (See Appendix 1B). In the diary, patients will record their adherence to the medication, if they had an episode of enuresis, as well as the number of nighttime awakenings specifically secondary to nocturia (and not for

any other reason such as pain or anxiety). All patients will have a follow up call two weeks and four weeks after starting the medication by the study coordinator. Patients will be assessed for improvement in symptoms, medication adherence, and any side effects they are experiencing. Blood pressure, Chem-10, Urine and serum electrolytes and osmolality and urine analysis will be obtained if patient describes any adverse clinical symptoms as would be performed as part of standard of care. Enuresis diaries will be reviewed, and if patients do not have at least a 50% improvement in symptoms they will be advised to make an appointment to investigate if adjustment of the medication based on clinical care would be appropriate. See Appendix 3 for a complete study timeline.

Any patient that has a dose dependent side effect to the medication will have the dose reduced promptly and appropriate clinical management and follow up. If a patient has an acute VOC while taking study medication and is on intravenous fluids, the medicine will be held during the acute event. Individuals will be asked at the end of the study if they had a pain crisis or acute chest syndrome during this intervention.

Be advised that the patients will have up to one year to complete the study. Although the study should only take 4 weeks the patient will not be removed from study unless their participation lasts longer than one year. Children with sickle cell disease frequently have admissions related to their chronic disease that may prevent them from completing study within the 4 week time period. The medication works immediately and a stop in the medication will not cause a decrease in effect of the previous or current doses.

Study tools:

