Promis Fatigue scale- PROMIS® instruments use modern measurement theory to assess patient-reported health status for physical, mental, and social well-being to reliably and validly measure patient-reported outcomes (PROs) for clinical research and practice. PROMIS instruments measure concepts such as pain, fatigue, physical function, depression, anxiety and social function. The Fatigue scale utilizes a 7-day recall period (items include the phrase "the past 7 days") with five responses. The responses span from never (0) to almost always (4). The Fatigue scale is a 10 item questionnaire whose scores can be approximated if a participant skips a question. A 10-item short form can be scored as long as the participant answered at least 5 items. The Pediatric PROMIS Fatigue scale has been validated for patients aged 8-17 years of age. The surveys will be administered at initiation of medication (week 1) and after completion of 4 weeks of medication. If patients stop and restart the medication the survey will be taken after 4 consecutive weeks of at least 50 % compliance with the medication. This will assess differences in the patients' perception of fatigue after starting the medication. Please see Appendix 4 for Promis Fatigue Scale.

Statistics:

For our study, success in treatment will be defined as a 50% reduction in bedwetting episodes. Our primary endpoint is the improvement in number of wet nights (binary outcome variable) comparing pretreatment and post treatment use of desmopressin. We can expect little or no change in untreated subjects and therefore presume that maximum 10% will improve on their own. Based on the study by Figueroa et al, we can presume that 60% of patients will improve

with desmopressin treatment. In order to detect this 50% difference, we will enroll 50 patients for the study so that the 95% CI for proportion of subjects with improvement after treatment is expected to be (0.46, 0.74) thus will be able to exclude 10% that is expected for untreated subjects. In a secondary analysis, the improvement status will also be correlated to patient characteristics using a logistic regression model. Secondary endpoints are not powered

 Magasi, S. et al. (2011). Content validity of patient reported outcomes: Perspectives from a PROMIS meeting. Quality of Life Research, 25 Aug 2011.

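### Must the plan fix a primary denominator and a missing-outcome rule before its expected interval of (0.46, 0.74) can stand?

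*Combined protocol and SAP*

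**What the plan says.** The Statistics paragraph defines success as halving the bedwetting episodes and presumes 60% success on desmopressin against at most 10% untreated. The size is set by precision: "we will enroll 50 patients for the study so that the 95% CI for proportion of subjects with improvement" should come out at (0.46, 0.74). No power, dropout allowance or analysis population is given.

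The secondary fatigue scale has an item-level missing-data rule in the study tools text: "A 10-item short form can be scored as long as the participant answered at least 5 items". It also has a rule for stopping and restarting. The primary wet-night count has neither.

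On how patients may leave, the Enrollment section says "Patients enrolled during hospitalization will not start the trial until a post-hospitalization follow up visit" and "Patients and/or guardians will have the option to decline participation or opt out of the study at any point". The Monitoring section notes that patients often "have admissions related to their chronic disease that may prevent them from completing study within the 4 week time period". The Background reports that in the earlier randomised phase "five participants completed the study and nine participants withdrew from the study".

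On how outcomes are obtained, Monitoring says "All patients will have a follow up call two weeks and four weeks after starting the medication by the study coordinator", and improvement is assessed at those calls. The Background says diaries "could be filled out retrospectively with study coordinator either in person or over the phone". Patients have up to one year to finish.

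On oversight, the Data Quality section sets a DSMC meeting once 20 patients are enrolled. The Data Safety and Monitoring Board section sets one once 20 have completed, and another at the end.

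**The concern.** The result is a single proportion from a single uncontrolled cohort, so the denominator carries the headline. With no rule written down, the choice between completers and all enrolled or treated patients could be made after the data are seen. A completers-only rate can be biased in either direction: upward if patients who do not improve abandon the diary, downward if patients who improve lose interest. It looks odd that the secondary scale has a missing-data rule and the primary endpoint has none, and the previous phase lost most of its participants. What would be at stake is the size of the reported benefit and, with heavy loss, the plan's one criterion of excluding 10%.

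The two DSMC triggers also look inconsistent. If the only safety review waits for 20 completers, it comes later than a meeting at 20 enrolled.

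**Working it through.** **Inputs from the plan:** n = 50, p = 0.60, reference 0.10, two-sided 95% (Statistics paragraph); 5 completed and 9 withdrew in the earlier phase (Background). **Assumed, because the plan gives no figure:** retention of 50% to 90%, and 60% improved among those observed.

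**1. The plan's interval.** Wald: p ± 1.96·√(p(1−p)/n) = 0.60 ± 1.96·√(0.24/50) = 0.60 ± 0.136 = (0.464, 0.736). This rounds to the printed (0.46, 0.74). At n = 44 it is (0.455, 0.745), which rounds to the same figures. Losing up to 6 of 50 (12%) therefore leaves the printed interval unchanged.

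**2. Three denominators.** With m patients observed, completers give 0.6m/m, missing as not improved gives 0.6m/50, and missing as improved gives (0.6m + 50 − m)/50.

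| Retention (assumed) | Completers | Missing as not improved | Missing as improved |
|---|---|---|---|
| 90% (m = 45) | 60% (0.46, 0.74) | 27/50 = 54% (0.40, 0.68) | 32/50 = 64% (0.51, 0.77) |
| 80% (m = 40) | 60% (0.45, 0.75) | 24/50 = 48% (0.34, 0.62) | 34/50 = 68% (0.55, 0.81) |
| 70% (m = 35) | 60% (0.44, 0.76) | 21/50 = 42% (0.28, 0.56) | 36/50 = 72% (0.60, 0.84) |
| 50% (m = 25) | 60% (0.41, 0.79) | 15/50 = 30% (0.17, 0.43) | 40/50 = 80% (0.69, 0.91) |

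Every lower limit exceeds 0.10.

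**3. Chance that an exact 95% interval excludes 10%.** With a denominator of 50 this needs at least 10 successes (exact lower limit 0.1003 at 10/50, 0.086 at 9/50). With missing as not improved, the chance is above 0.999 at 70% to 90% retention and 0.96 at 50%.

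**4. Stress case.** At the earlier phase's retention of 5/14, about 50 × 5/14 = 17.9 patients are observed. Completers (n = 18) give 60% (0.37, 0.83), with a 0.994 chance of excluding 10%. Missing as not improved gives 0.6 × 17.9/50 = 0.21 (0.10, 0.33), with a chance of only about 0.65.

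**5. Completer bias, illustrated.** True rate 60%, 80% retained overall. If 90% of responders and 65% of non-responders stay: 0.54/(0.54 + 0.26) = 67.5%. If 70% and 95% stay: 0.42/(0.42 + 0.38) = 52.5%.

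**6. Routes to a missing outcome.** Opting out and being enrolled in hospital but never starting are clear routes. Admissions are not: the plan mentions them to justify the one-year window, which keeps such patients in. The Risks section's assurance that a patient may have the drug without diaries or surveys follows directly on a sentence about refusing the study. It more naturally describes someone who is not among the 50.

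**7. DSMC.** The first trigger stands under a data-quality heading. The second belongs to a full review of safety, progress and efficacy. The two can coexist as separate meetings. If only the second is held, 20 completers need on average 20/0.8 = 25 enrolled at 80% retention or 20/0.5 = 40 at 50%. Meanwhile the Safety Monitoring section has Grade 3–5 events tracked in real time, and the hold rules send unexpected, possibly related serious events to the DSMC.

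**The case for a change.** The best case for a change is that a rule costs one sentence, needs no more patients and removes a choice that could otherwise follow the data. At an assumed 80% retention that choice spans 48% to 68%. The calls and retrospective diaries can supply outcomes, but nothing ties them to the primary analysis, says which weeks count after an interruption, or says what happens when recovery fails. At the earlier phase's level of loss, counting missing as not improved could miss the plan's own criterion.

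The omission stands, and so does the spread in the reported rate. The stress case is arithmetically right, but it comes from a blinded, placebo-controlled design that has since been abandoned, so it does not forecast an open cohort in which everyone is prescribed the drug. It also cuts against the most obvious remedy: under that loss it is the missing-as-failure rule that threatens the criterion, while completers do not. No rule follows from the document. Missing as not improved, a minimum number of recorded nights and an 80% retention figure would each be a new assumption or preference. The DSMC wording could be clearer, but no figure or safeguard depends on it.

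**Conclusion.** No change to the plan is called for. The expected interval is correct for 50 patients with an outcome and holds to two decimals down to 44. The conclusion it supports, that 10% is excluded, holds for all three treatments of missing outcomes at 50% to 90% retention, given 60% improvement among those observed. The weakest cell is 50% retention with missing as not improved, with a 0.96 chance. No stated figure or conclusion is shown to be wrong.

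What remains is an unwritten convention. Analysts ordinarily fill it by giving the numbers enrolled, treated and observed, and by setting the completer rate beside both extreme imputations; a reader can rebuild those bounds from the counts alone. Very heavy loss would make the denominator matter for the criterion too: at 9/14 lost, missing as not improved gives about 0.21 (0.10, 0.33). That would be visible in the reported counts. The two DSMC triggers are compatible as two meetings and amount to a point of clerical clarity.

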### **Risks/Assessment of Safety and Mitigation of Risks**

The overall incidence of adverse events with the use of desmopressin in patients with nocturnal enuresis is low. Reported adverse events are described as mild and transient, including headache, abdominal pain, nausea and dyspepsia. Adverse events report in patients treated with the intranasal formulations also included nasal congestion, rhinitis and epistaxis. The most serious, but uncommon adverse event is hyponatremia, which can induce seizures. This is reported more commonly with the intranasal formulation, but has also been noted with the tablet form. Robson et al looked at published data via Medline from December 1972 to August 2006 and post-marketing safety data from December 1972-June 2005 to assess the safety of desmopressin with a focus on the safety of the oral formulation. They identified 21 clinical trials on desmopressin use in children with nocturnal enuresis, in which there were no reports of hyponatremia. 21 publications were identified that included 48 case reports of hyponatremia, all of which were associated with intranasal desmopressin use. Post-marketing safety data reports identified 151 cases of hyponatremia in patients with nocturnal enuresis, 145 of whom were treated with the intranasal formulation and 6 of whom received the desmopressin tablet. Based on their review, Robson et al identified several preventable risk factors for hyponatremia, including avoiding high fluid intake, prescribing higher than recommended dose of medication, use of medication in patients younger than six years, and concomitant administration of another medication for nocturnal enuresis. They also recommend immediate discontinuing use of medication if patient develops symptoms of headache, nausea or vomiting, or if they develop an acute intercurrent illness, or are hospitalized and receiving IV fluids. Desmopressin package insert from Ferring Pharmaceuticals also recommends fluid restriction and recommend use with caution in patients with habitual or psychogenic polydipsia who may be more likely to drink excessive amounts of water, putting them at greater risk of hyponatremia.

In order to minimize the risk of an adverse event, patients will be given clear directions not to drink fluids after taking tablet. Patients will be advised to discontinue medication if they

Robson, W.L.M., et al., *The Comparative Safety of Oral Versus Intranasal Desmopressin for the Treatment of Patients with Nocturnal Enuresis*. The Journal of Urology, 2007. **178** (1): 24-30

 Desmopressin Acetate Package Insert

<http://www.fda.gov/downloads/advisorycommittees/committeesmeetingmaterials/pediatricadvisorycommittee/ucm215090.pdf>

develop symptoms of headache, nausea or vomiting and contact their doctor immediately. Doses used in the study are within the recommended range of 0.2-0.6 mg. Patients receiving another medicine for nocturnal enuresis (e.g. imipramine) will not be included in the study. Side effects of the medication will be monitored at each follow up visit.

Refusal to participate in the study including answering surveys will have no effect on the care that the child or the parent/caregiver receives. If the patient wants to be prescribed DDAVP and not complete the rest of the study (diaries, surveys), since this is standard of care medication it will still be prescribed and monitored as clinically indicated.

**Potential Benefits:**

There is the potential to benefit directly from improvement of their enuresis and with that potentially improved quality of sleep and hydration status, both of which may be key factors in mitigating vaso-occlusive crises.

**Data Safety Monitoring Plan**

**Data Quality**

Data quality will be monitored by the investigators and DSMC. The following elements will be monitored: recruitment proceeding as expected; study subjects match the inclusion/exclusion criteria; deviations from the protocol; adverse events; accuracy and confidentiality of all information both in the case report forms and electronic databases. DSMC will meet after the first 20 patients are enrolled to assess the quality of the data.

**Safety Monitoring**

Safety monitoring will be conducted by the investigators and DMSC. All adverse events will be indicated on the source documentation for the study, and on the specific adverse event case report form. The following information about adverse events will be collected: 1) the onset and duration; 2) severity or intensity; 3) relationship to study drug; 4) action taken 5) outcome. The investigators will determine the severity of the event, assign attribution to event, and monitor the event until its resolution. For the purpose of this trial, the following conditions are expected due to the subject’s underlying disease process or treatment and are not regarded as serious adverse events.

Expected AE due to sickle cell disease	Expected AE due to sickle cell disease	Expected AEs due to IVIG	Expected AE due to narcotic usage
---	---	---------------------------------	--

Acute chest syndrome	Hyperplastic bone marrow	Asthenia	Constipation
Anemia	Hypoxemia (pO 2 < 65 mm Hg)	Back pain	Hives
Aplastic crisis/anemia	Infection, encapsulated organism	Fever/Chills	Pruritus
Arthralgia	Jaundice	Cough	Respiratory depression
Avascular Necrosis of hip/shoulder	Leukocytosis	Headache	Urinary retention
Bone infarction	Meningitis	Hypertension	Nausea/vomiting
Cardiomegaly	Nausea and vomiting	Pharyngitis	
Cholecystitis	Pain, joints or long bones	Rash	
Cranial nerve palsy	Pain abdominal, chest, or back	Urticaria	
Decreased lung function	Priapism	Pruritis	
Delayed growth/puberty	Pulmonary hypertension	Dizziness	
Depressed ESR	Pulmonary infiltrates on CXR	Back pain	
Elevated serum bilirubin	Pyelonephritis	Arthralgia	
Elevated urinary urobilinogen	Renal papillary necrosis	Nausea/vomiting	
Fever	Reticulocytosis	Diarrhea	
Hand-foot syndrome	Retinal disease		
Hematuria	Retinal hemorrhage		

Hepatic sequestration	Rhabdomyolysis		
Hemolysis	Sepsis		
Hepatosplenomegaly	Skin ulcers		
Hyposthenuria	Splenic sequestration		

Adverse events (Grade 3-5 severity in the CTCAE of the latest version) will be actively tracked in real time on each patient.

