### **Intervention**

Patients if they meet eligibility criteria will be prescribed DDAVP starting at 0.4 mg every night. Baseline data will be obtained from all patients enrolled in the study using data from 6 months prior to initiating DDAVP. This includes medical history specific to SCD, general medical history (see Appendix 2A), baseline data and labs within the last 6 months (Appendix 2B-D). Renal sonogram will be obtained to assess baseline degree of fibrosis, unless patient has previous normal renal sonogram as part of standard of care.

The day that DDAVP is initiated, patients will complete the Promis Fatigue Scale to measure fatigue as a quality of life measure. We will repeat this questionnaire in a month after starting DDAVP.

Patients will receive 0.4 mg oral desmopressin tablet to be taken at bedtime and will receive similar instructions to take tablet at bedtime with minimal water. They will also be advised not to drink caffeinated beverages four hours before bedtime, not to drink any liquids after taking tablet, and to void right before bedtime. Patients will also be advised to discontinue medication if they develop symptoms of headache, nausea or vomiting, develop an acute illness, or if they are admitted to the hospital and are receiving intravenous fluids.

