**Trial will be put on hold if any of the following criteria are met:**

The trial will be put on hold (with no further subject enrollment and treatment) pending IRB and DSMC review if:

- 1) Cumulatively 2 patients experience an unexpected possibly related Grade 3 serious adverse event, or
- 2) 1 patient experiences an unexpected possibly related Grade 4-5 serious adverse event, or
- 3) 1 patient experiences an unexpected possibly related seizure episode of Grade 3 severity or higher.

The determination of whether the adverse event is definitely related to DDAVP or not will be made by the IRB, and DSMC and accordingly a decision to stop the trial completely or proceed will be made by both agencies. No study enrollment or treatment will occur while the triggering event is being reviewed.

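### The expected-event list includes IVIG effects, omits desmopressin, and on a literal reading keeps severe drug-related headache or vomiting out of the trial hold rule

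*Combined protocol and SAP*

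**What the plan says.** Three parts of the protocol bear on this point.

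- **Patient-level stop advice.** Under Intervention: "Patients will also be advised to discontinue medication if they develop symptoms of headache, nausea or vomiting". The Risks section says that "The most serious, but uncommon adverse event is hyponatremia, which can induce seizures", reports a published review's advice to stop for the same symptoms, and then tells patients to stop if they "develop symptoms of headache, nausea or vomiting and contact their doctor immediately".
- **Classification of events.** Safety Monitoring gives a table of conditions that, for this trial, are expected from the subject's "underlying disease process or treatment and are not regarded as serious adverse events". Two columns are for sickle cell disease, one is headed "Expected AEs due to IVIG", and one is for narcotic use.
- **Hold rule.** Criterion 1 is met when "Cumulatively 2 patients experience an unexpected possibly related Grade 3 serious adverse event". Criterion 2 needs one patient with an unexpected, possibly related serious event of Grade 4-5. Criterion 3 is met when "1 patient experiences an unexpected possibly related seizure episode of Grade 3 severity or higher".

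On laboratory work, Monitoring states: "Blood pressure, Chem-10, Urine and serum electrolytes and osmolality and urine analysis will be obtained if patient describes any adverse clinical symptoms".

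**The concern.** The protocol treats headache, nausea and vomiting as reasons for a patient to stop desmopressin and, in the Risks section, gives this advice in the context of hyponatremia. The table then labels the same symptoms as expected and not serious, whatever their grade. Since the hold criteria depend on those two labels, the warning signs used for the individual patient may be lost to the rule that protects the other participants. Part of the table also does not belong to this study: it lists effects of a product that is not given here and leaves out the product that is. At stake is whether a cluster of severe symptoms possibly caused by the study drug would pause enrollment and treatment in a trial that takes children from age 8.

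**Working it through.** The protocol gives no figure for how the hold rule performs, so the check compares the text of the table with the text of the rule.

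**Step 1: count the table entries (Safety Monitoring).**
- Sickle cell disease: 2 columns × 21 rows = 42 entries. Nausea and vomiting are included; headache is not.
- IVIG: 15 entries, 14 of them distinct because back pain appears twice. Headache and nausea/vomiting are both included.
- Narcotics: 6 entries. Nausea/vomiting is included; headache is not.
- Desmopressin: 0 entries.
- Hyponatremia or seizure in any column: 0 entries.

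Headache therefore has one source, the IVIG column. Nausea/vomiting has three.

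**Step 2: conditions in the hold rule.** All three criteria require an unexpected, possibly related event. Criteria 1 and 2 also require a serious adverse event. Criterion 3 does not, but applies only to seizure.

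**Step 3: apply the table literally to an event judged possibly related to desmopressin.**

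| Event as recorded | In table? | Criteria 1 and 2 | Criterion 3 |
|---|---|---|---|
| Headache, Grade 3 or higher | Yes, IVIG only | Fails on both unexpected and serious | Not a seizure |
| Nausea/vomiting, Grade 3 or higher | Yes, three sources | Fails on both unexpected and serious | Not a seizure |
| Hyponatremia, Grade 3 or higher | No | Can count if serious | Not a seizure |
| Seizure, Grade 3 or higher | No | Can count if serious | Can count |

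**Step 4: would deleting the IVIG column be enough?** No. Nausea/vomiting stays in the sickle cell and narcotic columns. The Risks section also names headache and nausea among reported desmopressin effects, so either could still be called expected with the column gone.

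**Step 5: effect on the design figures (Statistics).** The expected interval is 0.60 ± 1.96 × √(0.60 × 0.40 / 50) = 0.60 ± 0.136, or 0.464 to 0.736. This matches the stated (0.46, 0.74). Neither it nor n = 50 depends on the event list.

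**The case against.** The strongest reply is that the list is tied to cause. Each column names what the events are due to, and investigators must record relationship to study drug and assign attribution. A headache attributed to desmopressin is not an IVIG effect, and vomiting attributed to desmopressin is not a sickle cell or narcotic effect. On that reading the table does not exclude a possibly drug-related event. This is a fair reading, and it rules out the stronger conclusion a reader might draw, that such symptoms can never count or that their chance of causing a hold is zero. It does not settle the matter, because the introductory sentence covers every listed condition for the purposes of this trial and makes no exception for drug-related events.

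A second reply is that headache and nausea are known desmopressin effects and so expected in any case. The Risks section does name them, but as mild and transient; that does not support a not-serious label at Grade 3-5. The point does show that the IVIG column is not the whole cause.

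A third reply is that the real hazard is covered. Patients stop the drug and call their doctor, symptoms prompt electrolytes, Grade 3-5 events are tracked in real time, seizure has a one-patient hold, and the monitoring committee reviews all adverse events and can recommend ending the trial. All of this stands and limits the size of the problem. But the tracking has no stated trial-level action, and the Data Safety and Monitoring Board section schedules the committee only after the first 20 patients have completed and at the end.

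Listing vomiting as expected in this population is also a defensible way to avoid false holds. That argues for keeping the sickle cell and narcotic entries, not for applying them to events possibly caused by desmopressin.

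**Conclusion.** The text is wrong as written, with limited consequence. A safety table carries a column for a product outside this trial and nothing for the study drug. Taken literally, it works against the protocol's own stop signals, because severe headache or vomiting possibly due to desmopressin meets none of the three hold criteria. This rests on the literal reading; the attribution-based reading gives a different answer, and the protocol does not say which applies.

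A reader might infer that hyponatremia would go unnoticed or could not halt the trial. The documents do not support that. It is not on the list, electrolytes are drawn when symptoms are reported, and a serious case can count once identified. Nor can a probability of a missed hold be given, since the protocol states no rate for such events and describes overall incidence as low. The efficacy endpoint, the sample size and the interval are untouched.

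**What to change.** In Safety Monitoring, delete the IVIG column and add below the table:

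> The list applies only to events not considered possibly related to desmopressin. A Grade 3 or higher headache, nausea or vomiting possibly related to desmopressin that meets the criteria for a serious adverse event, and any symptomatic hyponatremia of Grade 3 or higher, is treated as an unexpected serious adverse event for the hold criteria.

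The first sentence settles the attribution question. The second prevents these events, including hyponatremia, from being classed as expected merely because the Risks section names them. The numerical thresholds in the hold rule stay as they are.

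The cost is one deleted column and two added sentences, with no extra visits, samples or patients. The downside is an occasional additional hold for review, during which enrollment and treatment stop.

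Repeating the contact-your-doctor advice under Intervention, and stating under Monitoring when the drug may be restarted after a symptom stop, would be useful but optional. The correction does not depend on either.
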